### 7.3.1.5. Administrative Status for Sayana®

Sayana® is provided by the investigator's prescription, and Pfizer Korea will not provide Sayana® for this study.

Record the following with regard to administrative status of Sayana®.

- Date of administration: Record the date of each Sayana® therapy (year/ month/day).
- Dose: Record the dose (ml).
- Outcome of administration:  
Record the evaluation date. If the purpose of administration was the prevention of pregnancy in women of child bearing potential, check either pregnant or not pregnant with the method of pregnancy check. If the subject is pregnant, record the first day of last menstrual period to collect the time to pregnancy. (At the time of first Sayana® administration, investigator must ensure the subject is non-pregnant. Also if a sexually active subject is having regular menstrual cycle and was previously not being administered with other contraceptive agent (therefore is having normal menstrual cycle), investigator must ensure that the first Sayana® injection is within 5 days of the subject's normal menstrual cycle. If the subject was previously being administered with other contraceptive agent(s) and is not having normal menstrual cycle, investigator must ensure that the subject is not pregnant by a method decided by the investigator).

If the purpose of administration was management of endometriosis-associated pain, visual analogue scale scores recorded by the subject.

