5.2 EFFICACY ANALYSIS SET

Subject who have been administered Sayana® at least once and evaluated upon its related efficacy endpoints at least once will be included in the efficacy analysis set. The efficacy analysis set is a subset of the safety analysis set.

The following cases are excluded from the efficacy analysis set:

- Subjects excluded from safety analysis set listed in section 5.1
- If the purpose of administration was the prevention of pregnancy in women of child bearing potential, subjects whose check either pregnant or not pregnant at evaluation date on the CRF are not completed
- If the purpose of administration was management of endometriosis-associated pain, subjects whose record VAS score at baseline or evaluation date on the CRF are not completed

Unless specified otherwise, statistical analysis on efficacy parameters will be performed on the efficacy analysis set.

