7 HANDLING OF MISSING VALUES

No imputation of missing data will be performed. Missing or incomplete data will be excluded from the analyses.

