8.2.2 Efficacy Analysis

The cumulative percent of patients who become pregnant by month 6 will be calculated as $100*(1 - \text{Kaplan-Meier curve at month 6})$, where the Kaplan-Meier (KM) method for estimating survival function will be applied to time-to-pregnancy. Patients who did not become pregnant will be censored at the time of their last follow-up. The KM method will also be used to calculate a 95% confidence interval for this cumulative percent at month 6.

[figure not shown]
[figure not shown]
The rate of pregnancies per 100 person-years of follow-up will be summarized by a 95% confidence interval.

For the rate of pregnancies per 100 person-years of follow-up defined as major events, incidence rate will be calculated as follows:

$100 \times (\text{total number of patients with effectiveness endpoint}) / (\text{total person-years of patients included in the effectiveness analysis set})$ where total person-years is equal to (last evaluation date of outcome - first date of administration +1)/365.25 for all patients in the effective analysis set

The difference between the visual analogue scale (VAS) endometriosis pain scores measured at each visit and the measurement taken before the administration of Sayana[®] will be analyzed using paired t-test.

PFIZER CONFIDENTIAL

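### The pregnancy rate in SAP 8.2.2 divides by person-years that include endometriosis-pain subjects, who have no pregnancy outcome field, so the contraceptive failure rate or its upper limit can be understated

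*SAP*

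**What the plan says.** **Rate.** SAP 8.2.2 defines the rate as 100 times the "total number of patients with effectiveness endpoint", divided by the total person-years of the effectiveness set. Each subject's time is given as "last evaluation date of outcome - first date of administration +1)/365.25 for all patients in the effective analysis set". No filter on purpose of administration appears in the numerator or the denominator.

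**Analysis set.** SAP 5.2 defines a single efficacy set, which I take to be the set that 8.2.2 calls the effectiveness set. A subject who was dosed at least once and "evaluated upon its related efficacy endpoints at least once will be included in the efficacy analysis set". The completeness rule depends on purpose. Contraception subjects need the pregnancy check. For endometriosis subjects, the rule removes those treated for "management of endometriosis-associated pain, subjects whose record VAS score at baseline or evaluation date on the CRF are not completed". An endometriosis subject with both VAS scores therefore stays in. The default is that "Unless specified otherwise, statistical analysis on efficacy parameters will be performed on the efficacy analysis set".

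**Outcome field.** Protocol 7.3.1.5 collects the pregnancy outcome by purpose: "If the purpose of administration was the prevention of pregnancy in women of child bearing potential, check either pregnant or not pregnant". For endometriosis-associated pain it collects only the VAS score.

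**Kaplan-Meier.** The cumulative-percent paragraph of SAP 8.2.2 names no population. It says only that "Patients who did not become pregnant will be censored at the time of their last follow-up".

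**The concern.** A rate needs its events and its time at risk to come from the same subjects, with the event looked for in all of them. Here an endometriosis subject contributes time up to her last outcome evaluation, which for her is a VAS date, while her effectiveness record has no place to mark a pregnancy. If the numerator is built from the outcome field, she can only add to the denominator.

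The numerator is not limited by purpose either. A pregnancy in an endometriosis subject would reach the CRF as an exposure during pregnancy (protocol 9.1 and 9.2.3), and the SAP does not say whether it counts. Two programmers could produce different rates from the same data.

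By the SAP 5.2 default, the Kaplan-Meier estimate would use the same set and censor endometriosis subjects as not pregnant.

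The study is descriptive and tests no hypothesis on pregnancy, so no decision changes. But both pregnancy measures are named effectiveness endpoints (protocol 7.1.2, SAP 6.2), and the estimates and intervals are what the study delivers to the regulator. SAP 8.2.1.3 already splits adverse events by purpose of administration; nothing does so for the pregnancy measures.

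**Working it through.** The documents give no expected rate, event count, person-years or split by purpose, so there is no planned figure to reproduce.

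**Inputs**
- From the documents: a minimum of 600 subjects (protocol 5 and 7.5), 6 months of observation (protocol 7.1), and a 95% interval based on the Poisson distribution (protocol 7.7.2.2).
- Assumed: full follow-up and no exclusions, giving 600 × 0.5 = 300 person-years (PY). The SAP's +1 day raises this only to about 600 × 183/365.25 = 300.6. 150 PY is shown as a lower case.
- Assumed: exact Poisson limits, since neither document names the method. Mid-P limits are shown as a check.
- Assumed: f, the endometriosis share of total person-time, and k, the number of pregnancies. k = 0 is the main case because the only prior figure in the documents is zero pregnancies in two earlier trials (protocol 5).

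**Formulas**
- SAP rate = 100 × k / PY.
- Contraception-only rate = 100 × k / [PY × (1 − f)].
- Limits on the count: lower = χ²(0.025; 2k)/2, upper = χ²(0.975; 2k + 2)/2. These are divided by the same person-years and multiplied by 100.
- If all k pregnancies are in contraception subjects, SAP value / contraception-only value = 1 − f, for the rate and for each non-zero limit, whatever the PY or the Poisson method.

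**No pregnancies: upper limit per 100 PY**

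The exact upper limit on the count is 3.689. The mid-P limit is −ln(0.05) = 2.996.

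| Case | SAP formula | f = 10% | f = 20% | f = 30% | f = 50% |
|---|---|---|---|---|---|
| 300 PY, exact | 1.23 | 1.37 | 1.54 | 1.76 | 2.46 |
| 150 PY, exact | 2.46 | 2.73 | 3.07 | 3.51 | 4.92 |
| 300 PY, mid-P | 1.00 | 1.11 | 1.25 | 1.43 | 2.00 |

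The columns by f are the contraception-only values. With exact limits, the gap at f = 10% is 0.14 at 300 PY and 0.27 at 150 PY. For SAP upper limit U, the gap passes 0.1 per 100 PY when f exceeds 1 − U/(U + 0.1). That is 7.5% for U = 1.2296 and 3.9% for U = 2.4593.

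**Three pregnancies, all in contraception subjects, 300 PY**

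The limits on the count are 0.619 and 8.767. The SAP formula gives 1.00 (0.21 to 2.92). Contraception-only:
- f = 10% (270 PY): 1.11 (0.23 to 3.25)
- f = 25% (225 PY): 1.33 (0.27 to 3.90)
- f = 50% (150 PY): 2.00 (0.41 to 5.84)

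**Three contraception pregnancies plus one endometriosis pregnancy, all counted, 300 PY**

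For k = 4 the limits on the count are 1.090 and 10.242, so the pooled rate is 1.33 (0.36 to 3.41). The contraception-only values are those just listed. The pooled point estimate is too high below f = 1 − 3/4 = 25% and too low above it. For the upper limit, the crossover is f = 1 − 8.767/10.242 = 14.4%.

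**Kaplan-Meier.** With no pregnancies the estimate is 0% in either population. Otherwise the effect depends on the censoring pattern, so I give no figure.

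**The case against.** The best defence is that the SAP can be read endpoint by endpoint. SAP 5.2 refers to each subject's related endpoints. In a pregnancy-rate formula the outcome date is naturally a pregnancy evaluation, which an endometriosis subject does not have. SAP 7 then says "Missing or incomplete data will be excluded from the analyses", which could remove her. This does not carry the rate. The phrase in 5.2 governs entry to the set, and 8.2.2 then sums over everyone in it. Protocol 7.3.1.5 records one evaluation date ahead of both outcome types, so both dates the formula needs are present. For Kaplan-Meier the SAP 7 reading is more plausible, which is a reason to state the population.

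Second, pregnancies in endometriosis subjects are not lost, because exposure during pregnancy must be recorded for any participant. Pregnancy is therefore captured in that group, but through safety reporting and not through a routine outcome check. If those cases are counted, numerator and denominator match in scope, since the protocol's endpoint wording says only patients. The rate then mixes two indications with different ascertainment. Preferring the contraception-only rate is partly a choice of estimand, and that much of the objection stands.

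Third, the size is assumed throughout. At f = 0 nothing changes. With no pregnancies only the upper limit moves. Because 600 is a minimum, person-years could exceed 300 and the absolute gap could be smaller; equally, discretionary visits and the exclusions in SAP 5.1 and 5.2 could make them fewer. All of this is right, but the ratio 1 − f does not depend on person-years.

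**Conclusion.** The concern holds: the denominator is wrong as written for a contraceptive failure rate. Followed literally, SAP 8.2.2 adds time from women whose effectiveness record has no pregnancy outcome.

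If only contraception-subject pregnancies are counted, the understatement is the fraction f, which is not in the documents. With no pregnancies the upper limit is the only informative part of the interval, and it looks more favourable than it should. If endometriosis-subject pregnancies are also counted, the direction is not fixed. The absolute figures rest on the assumed f, person-years, event counts and Poisson method. The ratio rests only on which pregnancies are counted.

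This should be fixed before the final analysis, although no decision rule is affected.

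**What to change.** In SAP 8.2.2, state that the numerator and person-years of the pregnancy rate, and the Kaplan-Meier risk set, are limited to effectiveness-set subjects whose recorded purpose of administration is prevention of pregnancy. List any pregnancy in an endometriosis-pain subject separately, outside both estimates.

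Align the protocol. Section 7.7.1.1 puts all analyses on the safety population, which does not match SAP 5.2, and sections 7.1.2 and 7.7.1.3 define the pregnancy endpoints without naming the purpose.

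No new data are needed. Purpose of administration is on the CRF (protocol 7.3.1.2) and is already a baseline subgroup variable (SAP 8.2.1.1 and 8.2.1.3). The work is one filter, a short addition to the SAP and a matching protocol edit. Protocol 7.7.2.2 calls for an amendment when primary endpoint definitions or analyses change in a major way. No endpoint is labelled primary, so the sponsor must decide whether that applies. The price is a wider interval and possibly a less favourable rate.

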#### 7.1.2. Effectiveness Endpoints

- Cumulative percent of patients who become pregnant over the 6 month observation period and rate of pregnancies per 100 person-years of follow-up.
- The patient response to endometriosis pain treatment: endometriosis pain treatment effect will be measured by visual analogue scale scores recorded by the subjects at each visit. The subject will be asked to indicate the subjective level of endometriosis pain looking back at the last 3 months and mark it with a single vertical mark on the 100mm horizontal visual analogue scale, where 0 mm represents absence of pain and 100mm indicates unbearable pain.

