### 7.3.1. Data Collection

The investigator will observe each enrolled subject for 6 months, prospectively, from the enrollment date. There is no specified visit schedule, because this study is not an interventional study. Safety information will be collected at every visit performed for the subject during the observation period.

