#### **7.7.2.2. Effectiveness Analyses**

- The cumulative percent of patients who become pregnant by month 6 will be calculated as  $100*(1 - \text{Kaplan-Meier curve at month 6})$ , where the Kaplan-Meier (KM) method for estimating survival function will be applied to time-to-pregnancy. Patients who did not become pregnant will be censored at the time of their last follow-up. The KM method will also be used to calculate a 95% confidence interval for this cumulative percent at month 6.
- The rate of pregnancies per 100 person-years of follow-up will be accompanied by an 95% confidence interval; this confidence interval will be based on the Poisson distribution.
- Mean change in VAS scores from baseline will be tested against zero change using the paired t-test; p-values  $\leq 0.05$  will indicate statistically significant change. Mean change will also be described using a 95% confidence interval.

Detailed methodology for summary and statistical analyses of data collected in this study will be documented in a SAP, which will be dated, filed and maintained by the sponsor. The SAP may modify the plans outlined in the protocol; any major modifications of primary endpoint definitions or their analyses would be reflected in a protocol amendment.

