2.1 STUDY DESIGN

This study is an open-label, non-comparative, observational, non-interventional, prospective and multi-center study in which subjects administered Sayana® (administered as part of routine practice in Korean health care centers by accredited physicians) will be observed prospectively for a period of 6 months from the enrollment date. The visit schedule or interval will be decided by the investigator.

Subject Enrollment

Subjects will be enrolled by continuous registration method. The investigators will assess all the subjects in their practice who receive at least 1 dose of Sayana® 104mg/0.65mL agreed to participate in this study by signing the 'data privacy statement'. All subjects enrolled should meet the usual prescribing criteria for as Sayana® per the local product document and should be entered into the study at the investigator's discretion.

PFIZER CONFIDENTIAL

A written, Pfizer and institutional review board (IRB)/independent ethics committee (IEC)-approved, informed consent (ie, Data privacy statement) must be obtained before initiating study procedures.

Subject selection

The eligibility of the subject will be evaluated. After inclusion of the subject and after obtaining written informed consent (ie, Data privacy statement) (prior to any procedure being performed) from the subject or subject's parents/ legal representative (as appropriate), the investigator or site staff will record the subject data into source documents and into a Case Report Form (CRF). Enrollment visit is the visit when subject signs on informed consent (ie, Data privacy statement). Following the baseline data collection , the visits are at the discretion of the investigator and may follow the local usual standard of care, however, the sponsor recommends safety and treatment data assessments at 3 month intervals (every 12~14weeks) at a minimum during the 6 months of participation. A Follow-up Call is to be conducted by investigator or delegated staffs at least 28 calendar days after the last administration of the study drug within the observational period in order to collect information on the occurrence of adverse events and concomitant medications.

[Inclusion criteria]

Patients must meet all of the following inclusion criteria to be eligible for inclusion in the study:

- 1) *Subjects or legally authorized representatives of pediatric subjects agree to provide written informed consent form (ie, data privacy statement).*

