5.1 SAFETY ANALYSIS SET

Subject who have been administered Sayana® at least once will be included in the safety analysis set.

[figure not shown]
The following exclusions from the Safety Analysis Set are to ensure that the subjects who are not providing data to the analyses but have some record of treatment do not over-inflate the denominator for the analyses.

The following cases are excluded from the safety analysis set:

- Subjects who have taken Sayana® prior to the contract date
-
- Subjects who didn't receive Sayana® for this study
- Follow-up failure: Subjects for whom adverse event status (Adverse Events status is unknown or missing in CRF) could not be established
- Subjects who violate the inclusion/exclusion criteria (see section 2.1)
- Subjects who were prescribed for other indications except indications in the local product document:
 - [Indications]
 - Prevention of pregnancy in women of child bearing potential
 - Management of endometriosis associated pain
- Subjects who violate the dosage
 - [Dosage]
Sayana® is injected under the skin into the front upper thigh or abdomen every 3 months (12 to 14 weeks).

Unless specified otherwise, safety summaries and analyses will be presented for the safety analysis set.

PFIZER CONFIDENTIAL

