8.2.1.1 Baseline Characteristics

Baseline characteristics for this study are defined as follows:

- Age[†] (≤ 19 years, ≥ 20 years and ≤ 29 years, ≥ 30 years and ≤ 39 years, ≥ 40 years and ≤ 49 years, ≥ 50 years and ≤ 59 years, ≥ 60 years and ≤ 69 years, ≥ 70 years)
- Weight
- Height
- Purpose of administration (Prevention of pregnancy in women of child bearing potential, Management of endometriosis associated pain)
- Medical history (Past, Present / Yes, No)
- Concomitant medication (Yes, No)
- Concomitant therapy (Yes, No)
- Total number of injections of Sayana[®] (1, 2, 3, 4, >4)
- Dose per injections of Sayana[®] (1 pre-filled syringe(2.25ml), Other)
- Paediatric status (<19 years, ≥ 19 years)

PFIZER CONFIDENTIAL

- Geriatric status (<65 years, \geq 65 years)
- Kidney disorder (Yes, No)
- Liver disorder (Yes, No)

† Age = Using the information recorded in CRFs

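### Both planned pregnancy estimates run over all follow-up whatever the date of the last injection; an on-treatment companion is cheap to add and would separate later pregnancies

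*SAP*

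**What the plan says.** Protocol 7.1.2 defines the contraceptive endpoint over observation time: "Cumulative percent of patients who become pregnant over the 6 month observation period and rate of pregnancies per 100 person-years of follow-up". Observation is fixed at six months from enrolment and does not depend on further injections. Protocol 7.3.1 states: "The investigator will observe each enrolled subject for 6 months, prospectively, from the enrollment date". SAP 2.1 repeats this.

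The analysis follows that definition. For Kaplan-Meier, Protocol 7.7.2.2 and SAP 8.2.2 share one rule: "Patients who did not become pregnant will be censored at the time of their last follow-up". For the rate, SAP 8.2.2 sets each woman's time as "last evaluation date of outcome - first date of administration +1)/365.25 for all patients in the effective analysis set", and the numerator is every patient with the endpoint.

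SAP 5.2 admits women who were "administered Sayana® at least once and evaluated upon its related efficacy endpoints at least once", so one injection and one evaluation are enough. SAP 5.1 gives the interval: "Sayana® is injected under the skin into the front upper thigh or abdomen every 3 months (12 to 14 weeks". It also excludes women who depart from the dosage, without saying whether stopping is such a departure. Protocol 7.3.1.5 collects the date of every injection and, for pregnant women, the first day of the last menstrual period (LMP).

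**The concern.** Neither estimate ends time at risk when the interval after the last injection has run out, at discontinuation, or at a change of method. Neither document plans a second estimate that does.

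Consider a woman with one injection who is evaluated at month 6. Her later weeks, and any pregnancy in them, go into the Sayana result. If she stopped in order to conceive and did so, she raises the pregnancy rate. If she changed to another contraceptive, her pregnancy-free weeks lower it. A reader of the report could not tell a pregnancy during the injection interval from one after stopping. Protocol section 5 cites earlier trials with zero pregnancies under perfect use, so even one such event would affect how the result reads.

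**Working it through.** **The plan's own figure.** There is none to reproduce. The 600 in Protocol 7.5 is a regulatory minimum, and the documents give no pregnancy, stopping or switching rate.

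**Inputs from the documents.** Follow-up is 6 months, taken as 26 weeks. The injection interval is 12 to 14 weeks. The size is 600. The interval for the rate is a 95% Poisson interval (Protocol 7.7.2.2).

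**Assumptions not in the documents.** All 600 use Sayana for contraception and all are evaluated at week 26. A fraction d of 20%, 40% or 60% has one injection only. The others have two injections, 12 or 14 weeks apart. The extra day in the SAP formula is ignored.

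**One woman.** With one injection, the time beyond the interval is 26 − 14 = 12 weeks (12/26 = 46%) or 26 − 12 = 14 weeks (14/26 = 54%). Two injections at the stated interval reach week 24 to 28, so nearly all the affected time comes from women who stop.

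**All women.** Total time is 600 × 26 / (365.25/7) = 299.0 person-years.

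- 14-week cut-off: share beyond = d × 12/26.
- 12-week cut-off: share beyond = d × 14/26 + (1 − d) × 2/26. The second term is weeks 24 to 26 in women with two injections.
- Zero-event upper limit = 100 × 3.689 / person-years, where 3.689 is the exact Poisson limit. Over all follow-up this is 1.23 per 100 person-years.

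| One injection only | Share beyond, 14 / 12 weeks | Person-years kept, 14 / 12 weeks | Zero-event upper limit, 14 / 12 weeks |
|---|---|---|---|
| 20% | 9% / 17% | 271.4 / 248.4 | 1.36 / 1.49 |
| 40% | 18% / 26% | 243.8 / 220.8 | 1.51 / 1.67 |
| 60% | 28% / 35% | 216.2 / 193.2 | 1.71 / 1.91 |

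If continuing women on a 12-week schedule have a third injection at week 24, the second term vanishes. The 12-week shares are then d × 14/26 = 11%, 22% and 32%.

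**Direction.** The SAP rate is (on-interval rate × time kept + later rate × time beyond) / 299.0. Assume d = 40% and an on-interval rate of 0.5 per 100 person-years, which corresponds to a 6-month risk of 0.25%.

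- Later rate 0: (0.5 × 243.8)/299.0 = 0.41 at 14 weeks, and (0.5 × 220.8)/299.0 = 0.37 at 12 weeks. The 6-month Kaplan-Meier risk is 0.20% or 0.18%.
- Later rate 5: (0.5 × 243.8 + 5 × 55.2)/299.0 = 1.33, and (0.5 × 220.8 + 5 × 78.2)/299.0 = 1.68. The 6-month risk is 0.66% or 0.83%.

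**One event.** A single pregnancy after stopping moves the rate from 0 (upper limit 1.23) to 1/299.0 = 0.33 per 100 person-years (0.01 to 1.86).

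**The case against.** The strongest reply is that the SAP does what the protocol asks. The endpoint is defined over the observation period and per person-years of follow-up, the setting is usual care, and the analysis is descriptive with no hypotheses or decision rules. This stands: the all-follow-up estimates are not an error, and an on-treatment estimate is an addition.

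A reader might infer that the plan scores women who stopped as if still protected, and so does not describe the effectiveness of Sayana. The documents do not support that. They give an injection interval and say nothing about how long one injection protects. Nor do they fix the direction of any bias. For the same reason 14 weeks cannot be the only cut-off.

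A reader might also take the SAP to expect women with one injection, since "Total number of injections of Sayana" is tabulated from 1 to more than 4. More than four cannot fit into 26 weeks at 12 to 14 week spacing, so these look like generic categories. With SAP 5.2 they show only that such women are admissible.

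The size is also open. Visits are at the investigator's discretion, and counted time ends at the last outcome evaluation. A woman who stops and is last evaluated by week 12 adds nothing beyond either cut-off. Some of the 600 may be treated for endometriosis pain. The shares above are therefore near an upper bound for each assumed stopping rate.

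The dosage exclusion in SAP 5.1 might remove some women whose injections lapse. Read that way, it would drop them entirely, including their weeks within the interval and any pregnancy in those weeks. It is an ambiguity to settle and does not replace a time cut-off.

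**Conclusion.** The point holds as a gap in what is reported. Both estimates run over all follow-up, neither is labelled so, and no companion separates pregnancies within the stated interval from later ones. Under the assumptions above, 9% to 28% of person-time lies beyond a 14-week cut-off and 17% to 35% beyond a 12-week one, and less if women who stop are not evaluated late. The stopping fractions and the assumed rates are illustrative, and the true size cannot be derived from the documents.

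It might be inferred that an on-treatment figure should become the main contraceptive result. The documents do not support that either, because it would displace the endpoint that the protocol defines. This is a cheap improvement that is worth making.

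**What to change.** - Keep the Kaplan-Meier percentage and the rate in SAP 8.2.2 as the protocol-defined results, and label them as all-follow-up.
- Add an on-treatment rate and Kaplan-Meier percentage. End each woman's time at the earliest of pregnancy, last outcome evaluation, and the end of the stated interval after her last recorded injection. Show both 12 and 14 weeks, described as analysis cut-offs and not as a claim about duration of protection.
- State in advance how a pregnancy is dated from the recorded LMP, count those within the window, and list later ones separately.
- State in SAP 5.1 whether stopping counts as a dosage violation.

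No new data are needed, since injection dates and LMP are already collected. The work is SAP wording and one derived end date per cut-off. Protocol 7.7.2.2 allows the SAP to modify the planned analyses, and the endpoint definition is unchanged.

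There are two downsides. Precision falls: the zero-event upper limit goes from 1.23 to between 1.36 and 1.91 per 100 person-years under the assumptions above. The on-treatment Kaplan-Meier estimate also assumes that stopping is unrelated to pregnancy risk. That is doubtful for women who stop in order to conceive, and it is a further reason to report both versions side by side.
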